2 STUDY OBJECTIVES AND ENDPOINTS

2.1 Primary objective

To evaluate the efficacy of osimertinib (AZD9291), in terms of the objective response rate (ORR) in patients with advanced non-squamous NSCLC with EGFR mutations and the EGFR T790M mutation at diagnosis, according to RECIST 1.1 criteria.

Primary endpoint: Objective Response Rate (ORR) which is defined as the Complete Responses [CR] or Partial Responses [PR] to treatment in accordance with the guidelines of RECIST version 1.1 criteria. An objective response should be confirmed at least 4-6 weeks after the initial response.

2.2 Secondary objectives

- To determine the safety and tolerability profile of osimertinib (AZD9291), measured using the number and severity of AEs entered into the Case Report Form (CRF); chemistry, blood count, vital signs, physical examination, weight, ECG and performance status (ECOG).
- To determine secondary efficacy parameters such as the progression-free survival (PFS), overall survival (OS), time to treatment failure (TTF), duration of response (DOR), disease control rate (DCR) and tumor shrinkage (TS).
- To correlate the parameters of clinical response efficacy documented with the EGFR mutational status.
- To carry out a longitudinal analysis of EGFR mutations (including the T790M mutation) in plasma and serum.
- To determine levels of BIM mRNA as well as mRNA levels of other biomarkers related to EGFR TKI response and determine whether they are predictors of treatment response.
- To identify mechanisms of acquired resistance to osimertinib (AZD9291); mutations at the site of covalent binding to the drug (C797) or other mutations in tissue or blood.
- To analyze biomarkers related to mechanisms of resistance to the treatment.

Secondary efficacy endpoints: Patient safety and adverse events will be assessed using the Common Terminology Criteria for Adverse Events (CTCAE) of the U.S. National Cancer Institute (NCI), version 4. Grade 3 or 4 adverse events and serious adverse events will be assessed to determine the safety and tolerability of the various combinations of drugs.

Secondary efficacy endpoints:

- The progression-free survival (PFS) is defined as the time from the start of the treatment to death or disease progression, assessed by the investigator in accordance with RECIST v1.1, regardless of whether the patient has discontinued the study treatment or is receiving treatment with another drug.
- Overall survival (OS) is defined as the time from the start of treatment to the time of death due to any cause.
- Time to treatment failure (TTF) is defined as the time from the start of treatment to the time at
 which the patient discontinues treatment due to any cause, including disease progression
 assessed by the investigator in accordance with RECIST v1.1, toxicity, death or at the
 patient's request.
- Duration of response (DOR) is defined as the time from the first documented response to documented disease progression or death, in accordance with RECIST 1.1 criteria.

Protocol date: May 21, 2018 Version 3

 Disease control rate (DCR) is defined as the percentage of patients with CR, PR or stable disease for a minimum of 24 weeks, assessed in accordance with the modified Response Evaluation Criteria in Solid Tumors (RECIST v. 1.1), version 1.1.

 Tumor shrinkage (TS) is defined as the percentage of tumor shrinkage from baseline (obtained from the sum of the largest diameters of the target lesions) according to RECIST v1.1 criteria.

Molecular secondary endpoints

- Correlation ratio of mutational status and documented clinical response.
- A progress curve showing the EGFR mutational status (including the T790M mutation) in plasma and serum longitudinally.
- Percentage levels of BIM mRNA as well as mRNA levels of other biomarkers related to EGFR TKI response.
- Percentage of patients with mutations at the site of covalent binding to the drug (C797) or other mutations in tissue and correlation ratio of documented clinical response.

3 STUDY OVERVIEW

3.1 Type of study

This is a multicenter, open-label, non-controlled phase IIa clinical trial.

3.2 Study design

The design of this study is divided into three well-defined phases:

Screening phase

During this phase, subject eligibility is determined, including the genotyping of the tumor and documentation of baseline characteristics. Considering that the study requires a sample of 73 patients with metastatic NSCLC (preferably women, with adenocarcinoma, former smokers or never-smokers) with activating EGFR mutations and concomitant T790M mutation, and bearing in mind that the estimated frequency of the concomitant T790M mutation in patients with metastatic NSCLC with activating EGFR mutations is 50% based on the frequency found in previous studies (Costa et al. 2010; Chen et al. 2016; Stahel RA, Dafni U, Gautschi O, et al. September 25-29; Costa et al. 2014), we estimate that it will be necessary to screen 146 patients with EGRF mutation to identify 73 patients with EGFR mutation and concomitant T790M mutation. This phase of the study will begin once the informed consent is signed by the patient, and the procedures to be performed are described in section 5 of the protocol.

• Treatment phase:

When a patient harboring both mutations is identified and the study screening criteria have been met, the patient will receive a dose of osimertinib (AZD9291) 80 mg every 24 hours, in tablets for oral administration. The study treatment will continue until one of the following situations arises:

Disease progression is confirmed radiologically and unequivocally, except for new
metastases in CNS or isolated progression of previously treated lesions in the CNS.
Patients who present disease control outside of CNS, defined as confirmed PR or CR of
any duration, or SD lasting ≥3 months, but who have developed metastases in CNS that
can be treated with radiation therapy, will be allowed to continue receiving study
treatment until they experience systemic progression of the disease outside CNS and/or
additional progression in the CNS that cannot be treated with additional radiation

Protocol date: May 21, 2018 Version 3

therapy

 Adverse event(s) which, according to the protocol or in the opinion of the investigator, can cause serious or permanent damage or which rule out further treatment with the study drug.

- General or specific changes in the patient's health state which, in the opinion of the investigator, make further treatment unacceptable.
- Major protocol non-compliance.
- Patient's withdrawal from the study.
- Death.
- Until the end of study, after a maximum of 78 weeks from the administration of the first dose of treatment by the last enrolled patient (see Section 3.7).
- Study is canceled by the sponsor.

In the event a dose change is required during the treatment, 40 mg tablets can be administered as described in section 6.9.

Treatment with osimertinib (AZD9291) is continuous, and every 21-day period will be considered one cycle. The treatment will begin on day 1 of the first cycle.

Follow-up visits will take place every 6 weeks to obtain basic safety data and every 12 weeks to obtain complete efficacy and safety data.

At the end of the study, patients may continue taking commercial osimertinib (TAGRISSO™) if it provides benefits in the investigator's opinion.

Follow-up phase:

Once the treatment phase is completed, a biopsy should be performed to identify acquired mechanisms of resistance to the drug and the follow-up phase will begin. The frequency of clinical assessments during this phase of the study will not differ from that performed in the course of standard clinical practice. Follow-up visits will take place every 12 weeks; information on the patient's health state will be included in the CRF, as well as any treatment received until the end of study.

3.5 Duration of study treatment (treatment phase)

The study treatment period is defined as the time elapsed between the first and the last dose of drug taken.

The study treatment should be discontinued if at least one of the reasons described in Section 3.2 occur, and the reason(s) for discontinuation will be recorded in the patient's history and in the corresponding case report form.

3.6 Duration of post-treatment follow-up period (follow-up phase)

The follow-up period is defined as the time elapsed from the last dose of treatment received and death, withdrawal of consent or end of study (EoS), whichever occurs first.

Protocol No.: MedOPP112 Protocol date: May 21, 2018

Version 3

3.7 End of study (EoS)

The EoS is defined as the Last Patient Last Visit (LPLV) at the end of the follow-up period. This is the last time point for data collection. It can be a clinical visit or a laboratory sample. The EoS will take place in a maximum of 78 weeks after the first dose administered to the last patient enrolled in the study.

However, the interim analysis will assess the primary objective and all the safety and efficacy objectives limited to a window of up to 42 weeks. After database lock at 42 weeks, patients will continue to be treated and controlled until the end of study date (see Section 8.6 Interim analysis).

4 PATIENT SCREENING

The following eligibility criteria can be used in the screening of patients for whom the protocol treatment is deemed suitable. In order to determine whether this protocol is suitable for a given patient, all medical and non-medical criteria should be taken into consideration.

4.1 Study Population

Patients diagnosed with stage EIIIB or IV non-small cell lung cancer harboring the EGFR activating mutation and concomitant T790M mutation who have not received prior treatment for this advanced disease will be enrolled in this study. Patients are not eligible if they are candidates for local curative treatment.

The analysis of EGFR mutational status (del19, L858R, L861Q or G719X) may be previously performed at each of the participating sites, but the tumor material taken from all patients should be submitted to the central laboratory for supportive analysis and T790M mutation analysis.

The patient's signed informed consent should be obtained before sending the tumor tissue sample to the central laboratory.

4.2 Inclusion criteria

Patient eligibility will be reviewed and documented by a suitable member of the investigator's study team before the patients are enrolled in the study.

Patients must meet all the following inclusion criteria to be enrolled in the study:

- 1. Patient aged 18 years or older.
- 2. Patients with histological confirmation of metastatic, non-squamous or locally advanced non-small cell lung cancer (NSCLC) who are not candidates for local curative treatment, with an activating EGFR mutation and concomitant T790M mutation.
- 3. Patients with an M1a stage according to the TNM version 7 including M1a (malignant effusion) or M1b (distant metastasis), or locally advanced disease that is not a candidate for

Protocol No.: MedOPP112 Protocol date: May 21, 2018 Version 3

curative treatment (including patients who progress after chemoradiotherapy in stage III disease).

- 4. Patients with an EGFR deletion or mutation in exon 19, exon 21 (L858R, L861Q) or exon 18 (G719X) and concomitant T790M mutation before treatment confirmed centrally.
- 5. ECOG (Eastern Cooperative Oncology Group) performance status less than or equal to 2.
- 6. Existence of measurable or evaluable disease (according to RECIST 1.1 criteria). Patients with asymptomatic and stable brain metastases are eligible for the study.
- 7. Possibility of obtaining sufficient tissue sample, via a biopsy or surgical resection of the primary tumor or metastatic tumor tissue, if no systemic treatment has been performed for advanced or metastatic disease from sample collection to enrollment in the trial.
- 8. Life expectancy ≥12 weeks.
- 9. Adequate hematologic function: Absolute neutrophil count (ANC) >1.5 x 109/L, platelet count >100.0 x109/L and hemoglobin >9.0 g/dL (>6.2 mmol/L).
- 10. Appropriate coagulation (INR ≤1.5).
- 11. Adequate liver function: Total bilirubin <1.5 × ULN, ALT and/or AST <2.5 × ULN, alkaline phosphatase <5 ULN, except in the presence of single bone metastases and in absence of any liver disorders.
- 12. Adequate renal function: Calculated creatinine clearance >50 mL/min (Cockcroft-Gault) and proteinuria <2+ (dipstick).
- 13. Capacity to swallow, patient capable of completing treatment and accessible, ensuring proper follow-up.
- 14. Patients able to complete study and within geographical proximity allowing for adequate follow-up.
- 15. Resolution of all acute toxic effects of previous anti-cancer therapy (which can only be adjuvant or neoadjuvant) or surgical interventions not exceeding grade 1 according to the NCI CTCAE version 4.0 (except for alopecia or other side effects that the investigator does not consider to be a risk to patient safety).
- 16. All men or women of childbearing potential must use a contraception method during the study treatment and for at least 12 months after the last dose of the study drug. Sexually active men and women of childbearing potential who are unwilling to use a contraception method are not eligible for the study.
- 17. The written informed consent (IC) must be signed and dated by the patient and the investigator before any study intervention takes place.

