5.2 Endpoints

(ICH E9; 2.2.2)

The efficacy study endpoints will be derived in accordance with Per Response Evaluation Criteria in Solid Tumours (RECIST v1.1) assessed by magnetic resonance imaging (MRI) or computed tomography scan (CT). The next endpoints have been defined:

Complete Response (CR): Disappearance of all target and non-target lesions and no new lesions.
Partial Response (PR): $\geq 30\%$ decrease in the sum of diameters of Target Lesions (TL) (compared to baseline) and no new lesions.

Stable disease (SD): Neither sufficient shrinkage to qualify as a response nor sufficient growth to qualify as progression.

Progressive Disease (PD): $\geq 20\%$ increase in the sum of diameters of TLs and an absolute increase in sum of diameters of $\geq 5\text{mm}$ (compared to the previous minimum sum) or progression of NTLs or a new lesion.

Not evaluable (NE): TL response is missing and there is no evidence of progression of NTLs and no new lesions.

BOR is the best response (by investigator assessment) a patient has achieved where the order of best to worst is CR, PR, SD, PD, NE prior to or at progression and prior to further anti-cancer therapy.

Additionally censoring strategies in time to event outcomes will be defined in accordance with Guidance for Industry Clinical Trial Endpoints for the Approval of Cancer Drugs and Biologics from food and drug administration.

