5.2.1 Primary endpoint

Confirmed objective response rate (cORR) is defined as the number of patients with complete response (CR) and partial response (PR), confirmed at least 4-6 weeks after the initial response, divided by the number of patients in the analysis set. Tumor response will be defined as best response, based on local investigator's assessment according to RECIST criteria guidelines (version 1.1).

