6.3.1 Inclusion criteria

Patient eligibility will be reviewed and documented by a suitable member of the investigator's study team before the patients are enrolled in the study.

Patients must meet all the following inclusion criteria to be enrolled in the study:

1. Patient aged 18 years or older.
2. Patients with histological confirmation of locally advanced or metastatic, non-squamous non-small cell lung cancer (NSCLC) with an activating EGFR mutation and concomitant T790M mutation who are not candidates for local curative treatment.
3. Patients with a M1a stage according to the TNM version 7 including M1a (malignant effusion) or M1b (distant metastasis), or locally advanced disease that is not a candidate for curative treatment (including patients who progress after chemoradiotherapy in stage III disease).
4. Patients with a EGFR deletion or mutation in exon 19, exon 21 (L858R, L861Q) or exon 18 (G719X) and concomitant T790M mutation before treatment confirmed centrally.
5. ECOG (*Eastern Cooperative Oncology Group*) performance status less than or equal to 2.
6. Existence of measurable or evaluable disease (as per RECIST 1.1 criteria). Patients with asymptomatic and stable brain metastases are eligible for the study.
7. Possibility of obtaining sufficient tissue sample, via a biopsy or surgical resection of the primary tumor or metastatic tumor tissue, within the 60 days prior to study entry.
8. Life expectancy \geq 12 weeks.
9. Adequate hematologic function: Absolute neutrophil count (ANC) $> 1.5 \times 10^9/L$, platelet count $> 100.0 \times 10^9/L$ and hemoglobin $> 9.0 \text{ g/dL} (> 6.2 \text{ mmol/L})$.
10. Adequate coagulation: INR ≤ 1.5 .
11. Adequate liver function: Total bilirubin $< 1.5 \times \text{ULN}$, ALT and/or AST $< 2.5 \times \text{ULN}$, alkaline phosphatase $< 5 \text{ ULN}$, except in the presence of single bone metastases and in absence of any liver disorders.

12. Adequate renal function: Calculated creatinine clearance > 50 mL/min (Cockcroft-Gault) and proteinuria < 2+ (dipstick).
13. Capacity to swallow, patient capable of completing treatment and accessible, ensuring proper follow-up.
14. Patients able to complete study and within geographical proximity allowing for adequate follow-up.

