7.4 Analysis populations

(ICH E3; 9.7.1, 11.4.2.5. ICH E9; 5.2)

Full Analysis and Safety analysis set (FAS)

Includes all included subjects who have received any study drug, independently of the degree of adherence to the protocol.

Per Protocol Set (PP)

The Per Protocol set includes all patients included in the FAS who did not violate the protocol in a way that might affect the evaluation of the effect of the study drug on the primary endpoint, i.e., without a major protocol violation.

Major and minor protocol violations will be identified by clinically trained personnel before the database lock. The definition of the major protocol violations is described in **Appendix 2**.

Biomarker analysis set

All patients included in FAS who has been evaluable for biomarker status.

Sensitivity analysis

Primary efficacy analysis will be performed on the full analysis (FAS) and PP sets. Secondary efficacy analysis will be performed on FAS. FAS will be considered the primary population for the efficacy analysis.

Biomarker analysis will be performed on biomarker analysis set.

Safety analysis will be performed on the full analysis set.

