Appendix 2 List of protocol deviations

Description	Category	Deviation excludes from analysis set?		
		Full Analysis / safety set	Per protocol set	Biomarker analysis set
Informed consent form not signed	Inclusion/Exclusion criteria	Yes	Yes	Yes
Outdated versions of informed consent signed	Inclusion/Exclusion criteria	Case by case	Case by case	Case by case
IMP no administered	Treatment	Yes	Yes	Yes
Without histological confirmation of locally advanced or metastatic, non-squamous non-small cell lung cancer (NSCLC).	Inclusion/Exclusion criteria	No	Yes	No
Without an activating EGFR mutation.	Inclusion/Exclusion criteria	No	Yes	Yes
Without concomitant T790M mutation.	Inclusion/Exclusion criteria	No	Yes	Yes
Patients without a M1a stage or M1b or locally advanced disease for which there is curative treatment	Inclusion/Exclusion criteria	No	No	No
ECOG>2	Inclusion/Exclusion criteria	No	No	No
No measurable or evaluable disease (as per RECIST 1.1 criteria). With the exception of pts with asymptomatic and stable brain metastases.	Inclusion/Exclusion criteria	No	Yes	No
Patients without having a pre-dose and a postdose valid result.	Biomarkers	No	No	Yes
Life expectancy <12 weeks.	Inclusion/Exclusion criteria	No	Case by case	No
Adequate organ function	Inclusion/Exclusion criteria	No	Case by case	No
Without capacity of swallow or complete the study.	Inclusion/Exclusion criteria	No	Case by case	No
No relevant toxicities at baseline	Inclusion/Exclusion criteria	No	Case by case	No
Patients who have received prior antineoplastic treatment for advanced disease.	Inclusion/Exclusion criteria	No	Case by case	No
Second active neoplasia	Inclusion/Exclusion criteria	No	Case by case	No

<6 months with prior treatment with cytotoxic chemotherapy for advanced NSCLC.	Inclusion/Exclusion criteria	No	Case by case	No
Patients who have received prior EGFR treatments for lung cancer.	Inclusion/Exclusion criteria	No	Case by case	No
Patients who have received treatment with an investigational drug within 3 weeks before the first day of study treatment.	Inclusion/Exclusion criteria	No	Case by case	No
Treatment with prohibited drugs within 14 days before the first day of study treatment.	Inclusion/Exclusion criteria	No	Case by case	No
Prohibited concomitant medication	Efficacy and safety	No	Case by case	No
Hypersensitivity to IMP	Investigational Medicinal Product	No	Case by case	No

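### Does counting patients without measurable disease in the confirmed response rate undermine the primary analysis?

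*Protocol*

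**What the plan says.** Protocol 4.2, item 6, asks for "Existence of measurable or evaluable disease (according to RECIST 1.1 criteria"), and SAP 6.3.1, item 6, for "Existence of measurable or evaluable disease (as per RECIST 1.1 criteria"). Neither requires measurable disease, and Protocol 5.2 has both measurable and non-measurable disease documented at screening.

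SAP 5.2 defines partial response as a fall of at least 30%, namely a "decrease in the sum of diameters of Target Lesions (TL) (compared to baseline) and no new lesions". Complete response is "Disappearance of all target and non-target lesions and no new lesions", which can be met without a target lesion.

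SAP 5.2.1 takes the number of confirmed responders "divided by the number of patients in the analysis set". The full analysis set in SAP 7.4 "Includes all included subjects who have received any study drug, independently of the degree of adherence to the protocol". SAP Appendix 2 removes from the per-protocol set a patient with "No measurable or evaluable disease (as per RECIST 1.1 criteria"), and qualifies even that: "With the exception of pts with asymptomatic and stable brain metastases". A patient with evaluable disease only is therefore in both sets.

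The subgroup comparisons in SAP 7.5 are by EGFR mutation type and biomarker level. None is by measurability at baseline.

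**The concern.** A response rate is easiest to interpret when everyone in the denominator could reach each response category. Here some patients may be unable to reach partial response by definition. If any were enrolled, the reported rate would fall below the rate in patients with target lesions. Comparing the full and per-protocol sets would not reveal this, since both keep these patients.

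Power would be at stake, and so would comparison with the published rates in Protocol 7.1, one of which is explicitly for patients with measurable disease. If the planning value of 70% were meant for patients with target lesions only, the true rate over all treated patients would be lower and the trial more likely to stop or fail wrongly.

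**Working it through.** **The plan's own figures.** Inputs from Protocol 7.1 and SAP 6.4: null rate 50%, alternative 70%, 21 patients in stage 1, stop at 11 or fewer responses, reject the null at 45 or more of 73. The probability of rejection at true rate p is

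sum over x = 12 to 21 of P(X1 = x; n = 21, p) × P(X2 ≥ 45 − x; n = 52, p).

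- p = 0.50 gives 0.0249 (stated: 0.025).
- p = 0.70 gives 0.9004 (stated: 90%).
- The probability of stopping at stage 1 is 0.668 at p = 0.50 and 0.068 at p = 0.70.

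The calculation depends on p only as the response rate among the patients counted. Nothing in it requires each patient to have a target lesion.

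**Which rate the plan targets.** Protocol 2.1 and SAP 5.1 set the objective as the response rate in patients with advanced non-squamous disease carrying both mutations. The hypotheses in Protocol 7.1 are stated for that population, without restriction to measurable disease. Objective, hypotheses, endpoint denominator and primary analysis set therefore agree. Counting a patient who cannot reach partial response as a non-responder also fits SAP 7.6, which treats missing responses the same way.

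**What a drop in power would require.** Let f be the share without a target lesion and c their complete response rate. Neither is in the documents. Suppose also, which the plan does not say, that 70% applies only to patients with target lesions. The full-set rate is then (1 − f) × 0.70 + f × c.

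| f | c | Full-set rate | Power |
|---|---|---|---|
| 0% | – | 70.0% | 90.0% |
| 5% | 0% | 66.5% | 77.2% |
| 10% | 0% | 63.0% | 57.2% |
| 10% | 20% | 65.0% | 69.3% |

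These losses come from moving the 70% to a different population. At a true full-set rate of 70%, power is 90% whatever f is.

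**Direction.** If the null rate of 50% also applied only to patients with target lesions, the full-set null with c = 0 would be 0.95 × 50% = 47.5% or 0.90 × 50% = 45%. The rejection probability would be 0.00865 or 0.00253, both below 0.025. The effect is conservative.

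**Size at the stage-1 number.** SAP 9 records that accrual closed after the interim review. The final number is not given, so 21 is used for illustration, with Clopper-Pearson 95% intervals.

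| Responders | All 21 | One non-responder left out | Two left out |
|---|---|---|---|
| 12 | 57.1% (34.0–78.2) | 60.0% (36.1–80.9) | 63.2% (38.4–83.7) |
| 14 | 66.7% (43.0–85.4) | 70.0% (45.7–88.1) | 73.7% (48.8–90.9) |

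Leaving out one patient moves the estimate by 60.0 − 57.1 = 2.9 points or 70.0 − 66.7 = 3.3 points. The full-set intervals are 78.2 − 34.0 = 44.2 and 85.4 − 43.0 = 42.4 points wide. If the patient left out had reached complete response, the 14-responder estimate would fall instead, to 13/20 = 65.0% (40.8–84.6).

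**The case for a change.** The best case for the concern is that every textual step is right: such patients are eligible, cannot reach partial response under SAP 5.2, remain in both analysis sets, and appear in no planned subgroup. Readers will compare the result with published rates, and the 62.1% cited from the gefitinib trial WJTOG3405 is labelled as measurable disease. With a small final sample, one or two patients move the estimate by 3 to 7 points.

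Those facts stand; they do not add up to a fault in the plan.

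- Only that one comparison is labelled as measurable disease. The 47% in patients with pre-treatment T790M, the figure closest to the 50% null, carries no such label.
- Some information is already planned. Tumor shrinkage is computed from target-lesion diameters, SAP 7.6 reports missing values for each endpoint, and SAP 7.12.2 shows the number of non-missing values beside each summary. This indicates how many patients have a target-lesion sum, though imperfectly, because missed scans also reduce the count.
- Protocol 5.2 expects selected lesions that can be followed at each assessment, which suggests few such patients but does not require measurable disease.
- A restricted analysis added now would come after open-label interim data were reviewed (SAP 9), with no separate statistical teams for the interim and final analyses (SAP 7.11.2). It would usually give the higher estimate.

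SAP 5.2 does not spell out the category for a stable patient without target lesions. Neither stable disease nor not evaluable is a response, so the primary endpoint is unaffected. The protocol's RECIST appendix, not available for this review, may settle it.

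**Conclusion.** The concern does not hold as a fault in the plan. Followed as written, the plan gives a sound estimate of the rate it sets out to estimate: confirmed response among all treated patients. Type I error (0.0249) and power (0.9004 at a true full-set rate of 70%) are as stated, and including patients without target lesions can only make a positive result harder to reach. The full-set rate would understate response in measurable disease if such patients were enrolled and responded less often, but the trial does not claim to estimate that quantity, and SAP 7.2 calls all efficacy analyses exploratory.

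This rests on reading the objective and hypotheses as covering the whole eligible population, which is what they say. The share of patients without a target lesion is unknown and may be zero. A count of them and a supportive rate in the remainder would be reasonable to report, but would change neither the primary analysis nor the decision rule.
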